## 2.2 Analysis sets

The **Screened** set will consist of all screened participants.

The **Randomized Analysis Set (RAS)** will consist of all participants who received a randomization number, regardless of whether participants received study medication.

The **Full Analysis Set (FAS)** will consist of all randomized participants who received at least one dose of study drug.

The **Safety Set (SAF)** will consist of all participants who received at least one dose of study drug. All analysis will be conducted on SAF except PK related analysis.

The **PK analysis set** will consist of all participants with at least one evaluable concentration data sample. All PK analysis will be conducted on PK analysis set.

### 2.2.1 Subgroup of interest

Below participants will be flagged at participants level for various analyses:

---

- Participants with subdural hematoma. This will be used for volMRI analysis.
- AEs indicative of neuro toxicity/peripheral neuropathy. This will be used for recovery analysis.

## **2.3 Patient disposition, demographics and other baseline characteristics**

Analyses for subject disposition, demographic characteristics, other baseline characteristics, will be summarized based on SAF by treatment group. Descriptive statistics of mean, standard deviation, minimum, median and maximum will be used for continuous variables. Frequency distributions will be used for categorical variables.

### **2.3.1 Patient disposition**

#### **Summary tables**

- The number and proportion of participants, who completed the study will be presented by treatment group.
- The number and proportion of participants who discontinued the study prematurely along with the primary reason for discontinuation will be presented by treatment group.
- The number and proportion of participants who discontinued the study drug prematurely along with the reason for the study drug discontinuation will be summarized and presented by treatment group.
- The number and percentage of participants in each analysis set described above will also be presented. Reason for screen failure will be summarized for all screen-failed participants.
- The number and percentage of participants with protocol deviations will be summarized by treatment group and following category:
  - Selection criteria not met
  - Participants not withdrawn as per protocol
  - Treatment deviation
  - Prohibited concomitant medication
  - Other deviations (important deviations that do not fall in the above four categories)

#### **Listings**

Listing will be provided for primary reason for early discontinuation.

### **2.3.2 Demographics and other baseline characteristics**

#### **Summary tables**

Patient demographics will be summarized with descriptive statistics for the SAF by treatment and overall. Parameters include:

- Age (at screening)

- Sex
- Race
- Ethnicity
- Height
- Weight
- BMI
- Educational level, years of education
- Smoking and alcohol history
- Country/region

Summary of HD history will include:

- CAG repeat length (larger allele from central lab)
- CAG age product (CAP) score defined as
  - Definition 1: CAP score = (length of CAG repeat – 35.0) × age at screening
  - Definition 2: CAP score = (length of CAG repeat – 30.0)/6.49 × age at screening
- Family history:
  - a Parent affected: (only) mother affected, (only) father affected, both parents affected, no parent affected, and unknown
- Age at clinical HD diagnosis (defined in [Section 2.1.1](#))

Other baseline characteristics:

- Unified Huntington's Disease Rating Scales (UHDRS)
  - Total Function Capacity (TFC)
  - Total motor score (TMS)
  - Independence scale (IS)

- mHTT protein in CSF
- volMRI by region

### **2.3.3 Medical history**

Medical history entered on the Medical History (MH) eCRF will be coded with the Medical Dictionary for Regulatory Activities terminology (MedDRA) using the most recent version at the time of reporting.

### **Summary tables**

Relevant medical history and current medical condition will be summarized by primary system organ class (SOC), preferred term (PT) and treatment group using the SAF.

## **2.4 Treatments (study treatment, rescue medication, concomitant therapies, compliance)**

### **2.4.1 Study treatment / compliance**

The SAF will be used for the below analyses.

### **Summary tables**

- Duration of total follow-up time (including both on and off treatment period) will be summarized descriptively by number of weeks.
- Duration of exposure to study drug (only on treatment period) will be summarized descriptively by number of doses and in days.

The investigational drug is applied as a weekly dose. Exposure in days will be calculated by the number of doses taken  $\times$  7 days using category ( $\geq 1$  mos,  $\geq 2$  mos.,  $\geq 3$  mos.,  $\geq 4$  mos.,  $\geq 5$  mos.. etc.).

### **Figures**

- Follow-up time (in weeks) will be displayed graphically for each individual, color coded by treatment group and using different shades for on and off treatment.

### **Listings**

## **2.4.2 A listing showing exposure in doses and days. Prior, concomitant and post therapies**

Please refer to [Section 2.1.1](#) for the definition of prior and concomitant medication.

### **Summary tables**

- The number and percentage of participants receiving concomitant medications and significant non-drug therapy will be summarized using the SAF by ATC class and preferred term (according to the World Health Organization drug dictionary (WHO-DD), including Anatomical Therapeutic Chemical (ATC) classification code, using the most recent version at the time of reporting), by treatment group and overall.
- Prior medication and non-drug therapies will also be summarized in a similar way.

## **2.5 Analysis supporting primary objective(s)**

Due to the early termination, the primary estimand and statistical modelling for dose-response relationship is no longer applicable. Primary endpoint of mHTT in CSF will be summarized descriptively. No sensitivity analysis or supplementary analysis will be performed.

The other primary endpoint safety and tolerability will be detailed the safety [Section 2.7](#).

### **2.5.1 Primary endpoint(s)**

### **2.5.2 Statistical hypothesis, model, and method of analysis**

The efficacy primary endpoint is the % change from baseline of mHTT protein concentration in CSF at week 17, which is expressed as:

$$(mHTT_{wk17} - mHTT_{baseline}) / mHTT_{baseline} * 100\%$$

#### **Summary tables**

- Summary statistics of raw, change, % change and annualized % change by visit
- Difference between active and placebo for % change by visit
- Mean time (in days) from last dose to lumbar puncture (LP) for week 9 and 17 (protocol scheduled visit window will be used to derive week 9 and week 17)

Days from last dose to LP = date of {LP} - date of {previous dosing date}

Note, if a dose is taken on the same day of LP performed, the previous dosing date should be used instead of the same day.

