2.1 Primary estimands

As per the USM follow-up notification dated 06-Dec-2022, the original estimand definition for dose-response relationship is no longer applicable due to permanent discontinuation of study treatment, and no dose-response modelling will be done. The primary endpoint mHTT in CSF will be summarized descriptively as specified in [Section 12](#).

The clinical question of interest is the effect of branaplam versus placebo on percent reduction of mHTT protein in CSF from baseline to Week 17 when the assigned treatment had been taken over 16 weeks with only limited interruptions or discontinuation (as defined below) in patients with manifest HD, mHTT protein in CSF above a detectable level, and a UHDRS TFC score of >8.

The primary estimand is described by the following attributes:

1. Population: male or female patients with confirmed Stage 1 or 2 HD (manifest), mHTT protein in CSF above detectable level, and a UHDRS TFC score of >8 in line with protocol defined I/E criteria. Further details about the population are provided in [Section 5](#).
2. Primary variable: change from BL (%) to Week 17 in mHTT protein in CSF.
3. Treatment of interest: the randomized treatment (allowed medication and prohibited medication see [Section 6](#)) taken for the DRF period (16 weeks of treatment) with a maximum of 25% missed doses (i.e., 4 doses for weekly dosing during DRF period) AND less than 2 consecutive weeks off treatment prior to the Week 17 visit LP.

Handling of remaining intercurrent events:

- Treatment discontinuations or interruptions of dosing beyond acceptable limits for any reason: the treatment effect will be imputed as if the treatment had continued or dosing had not been interrupted (hypothetical strategy). The limit is reached if one or both of the criteria below are met:
 - >25% missed doses (i.e., > 4 doses for weekly dosing during DRF period)
 - 2 or more consecutive weeks off treatment prior to week 17 (LP)
- Intake of prohibited medications without discontinuation of study drug: the treatment effect will be imputed as if the prohibited medications had not been taken (hypothetical strategy)

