After study treatment discontinuation, the participant should be followed for a period of 30 days. The following data should be collected at unscheduled site visits (if needed) or via telephone contact:

- New / concomitant treatments
- Adverse Events / Serious Adverse Events

The Investigator must also contact the IRT to register the participant's discontinuation from study treatment.

If discontinuation occurs because treatment code has been broken, please refer to Emergency breaking of treatment code section.

Premature discontinuation of study treatment during Core Period:

- If a participant prematurely discontinues study treatment before or at Week 17 visit during the DRF period (for reasons other than withdrawal of consent), all assessments corresponding to all visits during the DRF period should still be completed up to and including Week 17 as described in the visit evaluation schedule [Table 8-2](#), [Table 8-3](#) and [Table 8-4](#)).
- If a participant prematurely discontinues study treatment during the blinded extension after the Week 17 visit during the DRF period (for reasons other than withdrawal of consent) and therefore does not continue in the OLE, all assessments as described under the EOT/Week 53 visit in the VES should be completed during the last visit.

Any participant that discontinues study drug treatment at any given timepoint during the Core period should complete the EOT-Core Disposition CRF.

- Participants that prematurely discontinue blinded study treatment during the Core period and do not continue in the OLE study period must be followed up for safety for 30 days after the last dose of blinded study drug is administered.
- Participants that complete the blinded study treatment during the Core period and continue in the OLE study period, will be monitored for safety during the OLE while taking the selected open label dose.

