### On/off treatment

On treatment flag will be created for efficacy and safety endpoints including sNFL, volMRI, clinical endpoints, Nerve Conduction Studies (NCS), neuro exam, neuropathy symptoms [REDACTED] at visit level. An assessment is defined as on treatment if the collection date  $\leq \{ \text{last dosing date} + 13 \}$ . An assessment is defined as off treatment if the collection date  $\geq \{ \text{last dosing date} + 14 \}$ .

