#### Summary tables

- Summary statistics of raw, change, % change and annualized % change by visit and by on/off trt and by brain region

- Repeat after excluding Participants with subdural hematoma

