### **2.11.2 mHTT in CSF**

#### **Summary tables**

- Summary statistics of raw, change, % change and annualized % change by visit
- Difference between active and placebo for % change by visit
- Mean time (in days) from last dose to LP for week 9 and 17 (protocol scheduled visit window will be used to derive week 9 and week 17)

Days from last dose to LP = date of {LP} - date of {previous dosing date}

Note, if a dose is taken on the same day of LP performed, the previous dosing date should be used instead of the same day dosing.

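### CSF mHTT is summarised by visit with no on/off-treatment rows, so any lumbar punctures taken 14 or more days after the last dose would be pooled into the Week 9 and Week 17 means

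*SAP*

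**What the plan says.** SAP 2.5.2 defines the efficacy primary endpoint as the percent change in CSF mHTT from baseline to Week 17. Its tables are "Summary statistics of raw, change, % change and annualized % change by visit" and "Difference between active and placebo for % change by visit", and SAP 2.11.2 lists the same two. Neither mentions treatment status at the time of the LP. Both sections also plan the mean number of days from last dose to LP at Weeks 9 and 17.

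SAP 2.1.1 (On/off treatment) says: "On treatment flag will be created for efficacy and safety endpoints including sNFL, volMRI, clinical endpoints, Nerve Conduction Studies (NCS), neuro exam, neuropathy symptoms", followed by a redacted item. A collection up to 13 days after the last dosing date counts as on treatment. "An assessment is defined as off treatment if the collection date" falls 14 or more days after it. For volumetric MRI, SAP 2.6.2.2 plans "Summary statistics of raw, change, % change and annualized % change by visit and by on/off trt and by brain region". SAP 2.11.1 splits serum NfL the same way, but not CSF NfL.

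For participants who stop drug during the dose-range-finding period, Protocol 9.1.1 says "all assessments corresponding to all visits during the DRF period should still be completed up to and including Week 17". SAP Table 5-8, the visible window table for LP biomarkers (its title is partly redacted), maps Days 2 to 85 to Week 9 and Days 86 to 169 to Week 17. SAP 2.5 plans no sensitivity or supplementary analysis of mHTT, and 2.5.3 marks intercurrent events as not applicable.

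**The concern.** The by-visit mean is naturally read as the lowering achieved by taking 56 mg weekly. If some of the LPs behind it were taken after dosing had stopped, and mHTT recovers once drug is withdrawn, the active mean and the active-placebo difference move toward zero and the table does not show why.

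This matters more here than for a typical biomarker. SAP 2.6.2 says total HTT in CSF and the plasma HTT measures will not be reported because of assay problems. CSF mHTT at 56 mg is then the only HTT-lowering result planned for the study report, at the only dose tested. The SAP already has a rule for telling on-drug from off-drug assessments, but these tables do not use it.

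**Working it through.** **The plan's own figures.** The only design calculation for this endpoint is the power of the MCP-Mod test, since withdrawn (Protocol 12.8.1: above 80% on average). With doses 0/56/112/154 mg, n = 15/20/20/20, a maximum effect of 0.35 and one-sided 5%, mean power over the five candidate curves is 0.939 with a common SD at effect size 1, and 0.890 with the stated SDs of 0.471 and 0.195. The statement reproduces, but it has no bearing on a descriptive table. The relevant figure is the approximate 30% steady-state CSF lowering at 56 mg in the Amendment 02 rationale. It is an estimate, not a Week 17 mean, and the documents give no data from which to re-derive it.

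**Can off-drug LPs enter the tables?**
- Early discontinuers are asked to complete Week 17 (Protocol 9.1.1). Participants on hold for toxicity continue all assessments except dosing (Protocol 6.5.2).
- The Week 17 window is 169 − 86 + 1 = 84 days wide.
- Against this, the 05-Aug-2022 urgent safety measure (USM) ended further LPs unless the investigator judged one necessary, the last dose in the trial was on 08-Aug-2022, and the post-USM schedule (Protocol Table 8-5) contains no LP.

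So such LPs are possible but limited. No section counts them.

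**How far would they move the mean?** Let f be the share of active LPs taken off drug and r the share of the lowering still present. Both are assumptions, because the documents give neither a count nor a washout rate.

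Observed lowering = 30% × [1 − f(1 − r)]

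| f | r = 0 | r = 0.5 | r = 0.75 |
|---|---|---|---|
| 0% | 30.0% | 30.0% | 30.0% |
| 10% | 27.0% | 28.5% | 29.25% |
| 20% | 24.0% | 27.0% | 28.5% |
| 30% | 21.0% | 25.5% | 27.75% |
| 50% | 15.0% | 22.5% | 26.25% |

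At the planned cohort size of 25 randomised 4:1 (20 active), one off-drug LP shifts the mean by 30 × (1 − r)/20, which is at most 1.5 percentage points.

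The value of r depends on time off drug. With an assumed recovery half-life of h weeks, r = 0.5^(t/7h), with t in days. For h = 2 to 6, r is 0.50 to 0.79 at 14 days, 0.25 to 0.63 at 28 days and 0.06 to 0.40 at 56 days. An LP just past the 14-day limit would therefore matter little, and one two months out would matter much more.

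**Does the planned interval table deal with it?** A pre-dose LP on schedule is 7 days after the previous weekly dose. Suppose, for illustration, 18 LPs at 7 days and 2 at 42 days. The mean is (18 × 7 + 2 × 42)/20 = 210/20 = 10.5 days, inside the 13-day limit although 10% of the LPs are off drug. The mean can therefore look reassuring when values are affected, and it cannot separate them.

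**The case against.** The strongest case for the plan is that the pattern is coherent. The tables that are split are MRI and serum NfL, which continued off drug to Week 69. The CSF measures, NfL as well as mHTT, are not split, and LPs essentially stopped with dosing. The sponsor did consider the interval from dose to LP and plans to report its mean. Individual percent change is plotted at actual weeks (SAP 2.5.2), and each participant's on- and off-treatment follow-up is charted (SAP 2.4.1). The flag list is open-ended and has a redacted item, so the flag itself may cover mHTT. All of this stands. It narrows the point to the table layout and to a probably small number of LPs. It does not supply the missing rows.

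A second objection is that an on-treatment comparison conditions on a post-randomisation event, in a trial stopped for neurotoxicity. It would also be chosen after sponsor unblinding on 02-Nov-2022 (Protocol 6.4) and the April 2023 interim analysis (SAP 2.13). This too stands, and it is the reason not to make the on-treatment row the main result.

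A reader might also infer that the SAP silently dropped a protocol rule excluding LPs taken two or more weeks off drug. The documents do not support that. The pre-USM estimand handled such cases by a hypothetical strategy with imputation, not exclusion, and Protocol 2.1 and 12.4 themselves withdrew it.

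**Conclusion.** The CSF mHTT tables cannot distinguish on-drug from off-drug LPs, although the SAP already defines the distinction and applies it elsewhere. Any off-drug LP in the active group would be expected to pull the reported lowering toward zero. The size is unknown. Under the assumed ranges, a 30% lowering reads 27.0 to 29.25% with 10% of LPs off drug and 21.0 to 27.75% with 30%; with none, nothing changes.

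It would be tempting to conclude that the Week 17 result is diluted. The documents do not show this, because no off-drug Week 17 LP is recorded and the USM left little room for them. The conclusion rests on three things: mHTT recovering after withdrawal, some LPs having been taken 14 or more days after the last dose, and the tables being produced as written. The issue affects interpretation only, as no test or error rate depends on it. It is an inexpensive improvement, not a flaw that invalidates the summary.

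**What to change.** Keep the all-LP by-visit summary and active-placebo difference in SAP 2.5.2 and 2.11.2 as the main presentation. Beside them, at Weeks 9 and 17, using the existing flag in both arms, add:
- N, percent change and the active-placebo difference for on-treatment LPs (collected no later than last dose + 13 days);
- N and percent change for off-treatment LPs.

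Report the minimum and maximum, as well as the mean, of days from last dose to LP. State in a footnote whether the flag's last dosing date is the final dose or the most recent dose before the LP. The interval formula already uses the previous dose, and the two differ for a participant whose dosing was interrupted and resumed.

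The cost is one existing flag applied to one more variable. The downsides are small cells, especially for placebo (about 5 of 25 at 4:1), and an on-treatment row that is not a comparison as randomised. Label that row accordingly, note that it was added after unblinding, and do not let it replace the all-LP summary. If no LP is off treatment, the added rows will show that.

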#### **Figures**

- Spaghetti plot of % change over time (using actual weeks)
- Mean % change over time (using scheduled weeks) and error bar (standard error) by treatment group (group average and N will be added on x-axis)

### **2.5.3 Handling of intercurrent events**

Not applicable.

### **2.5.4 Handling of missing values not related to intercurrent event**

The missing values will be treated as missing. Unless otherwise stated, missing data will not be inputed for the analysis.

## **2.6 Analysis supporting secondary objectives**

### **2.6.1 Secondary endpoint(s)**

The secondary objective is to assess

- The pharmacodynamics (PD) of branaplam in participants with HD on clinical, imaging and biomarker endpoints relevant to HD.
- The pharmacokinetics (PK) of branaplam and its metabolite UFB112 in plasma and CSF

### **2.6.2 Statistical hypothesis, model, and method of analysis**

Secondary endpoints include:

- Clinical endpoints: Unified Huntington's Disease Rating Scale (UHDRS) Total Functional Capacity (TFC), UHDRS Total Motor Score (TMS), UHDRS Independence Scale (IS)

- Vol MRI: Ventricular, Caudate and Total Brain Volume
- PK: branaplam and its metabolite UFB112 in plasma and CSF.
- The biomarker secondary endpoints (total HTT in CSF, [REDACTED] plasma, and mHTT in [REDACTED] plasma) will NOT be reported due to assay issues with the vendor.

### 2.6.2.1 Clinical endpoints

#### Summary tables

- The clinical endpoints will be summarized with appropriate descriptive tables by visit, and treatment group.

#### Figures

- Average change from baseline with error bars (standard error) will be provided by group (group average and N will be added on x-axis)

### 2.6.2.2 Volumetric MRI

In order to assess atrophy rate, volMRI images from follow-up timepoints are compared to those from earlier timepoints using the boundary shift integral (BSI) technique in selected brain regions. The technique determines the total volume through which the boundaries of a given cerebral structure have moved, and hence, it aims at quantifying the amount of change in these selected brain regions. Absolute volume is provided using Medical Image Display and Analysis Software (MIDAS). BSI change is provided by vendor directly in the database, % change and annualized % change will be derived using BSI change and baseline from MIDAS. The output of the method is a change from BL in volume (atrophy). The direction of change (BSI) varies by region as illustrated in [Table 2-1](#).

**Table 2-1 BSI measuring atrophy by region**

Region	Sign	direction of change
Whole brain	+	mean atrophy, ie volume reduction
Ventricles	+	ventricular expansion, ie volume increase
Caudate	+	mean atrophy, ie volume reduction

For all the volMRI analyses, the QC failures (QCgrade= “Failed”) should always be excluded. For ADaM data, the sign will be unified for BSI such that “-“ always indicates atrophy (ie a volume reduction), and “+” always indicates an expansion (ie a volume increase) across regions.

Flags:

- on/off treatment flag will be derived at visit level
- Participants with subdural hematoma (from AE panel).

